## 8.3 Study procedures

### **Expectation induction**

Expectations will be induced by conditioning and verbal suggestion procedures with regard to two specific colored cues being displayed on a computer screen. For half of the participants the first colored cue is the conditioned cue and the second colored cue is the neutral cue, and visa versa for the remaining participants. In part I of the experiment the high- itch expectation induction procedure, as described below, is applied for all participants. In part II, participants are allocated to one of the three experimental groups in which either the low-, high-, or neutral expectation induction is applied (see section 3. Study design and Fig 1.).

High-itch expectation induction

For the high-itch expectation induction, the intensity (mA) of the stimuli will be increased following the presentation of the conditioned cue (*expectation for high itch*) in comparison to the intensity of stimuli following the neutral cue, which is not adjusted (*neutral expectation*). In line, participants will be told that: "The specific colored cue will signal the activation of the third electrode that induces an increase in the intensity of the itch stimulus (*expectation for high itch*). The other cue will indicate that the third electrode is turned off and will not change the intensity of the itch stimulus (*neutral expectation*)".

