Main study parameters/endpoints: The main study endpoint is the difference in the levels of itch (VAS scores) evoked by the electrical stimuli associated with the conditioned cues versus the neutral cues in the testing phase of part II of the experiment. It is investigated whether nocebo effects (negative expectation effects) can be modified by a positive expectation induction by conditioning and verbal suggestion (low-itch expectation induction) (group 1), resulting in lower itch VAS scores than a repeated negative expectation induction (high-itch expectation induction) (group 2), or a neutral procedure (neutral expectation induction) (group 3).

Nature and extent of the burden and risks associated with participation, benefit and group relatedness: Participants will complete a series of validated questionnaires at home to assess relevant individual characteristics, for approximately half an hour. Participants will then visit the department of Health-, Medical & Neuropsychology at the Leiden University once for approximately 5,5 hours. Sensations of itch will be induced using frequently applied, validated stimuli of short duration which are not burdensome (e.g., [1-4], 25). DNA is collected by asking participants to spit in a special tube. No risks are involved with participation in this study, only an investment of time.

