#### Part II

#### Group 1: Low-itch expectation induction

Participants in this group will receive a low-itch expectation induction regarding electrical stimuli by conditioning with verbal suggestion. A conditioning procedure will be applied in which the same specific colored cue as described above displayed on a computer screen (conditioned cue) is repeatedly associated with a decreased intensity of the itch stimulus. In line with the conditioning procedure, verbal suggestions for low itch will be given regarding the itch stimuli.

[figure not shown]

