### 4.4 Sample size calculation

The required sample size was calculated, in agreement with a statistician ([name], Radboudumc), based on our previous study with a comparable design [25]. Such as in the present study, in our previous study a comparison was made between a positive expectation induction by conditioning and verbal suggestion and a control group. In this study an average placebo effect of 0.86 (SD = 0.59) and 0.32 (SD = 0.79) was found in the *conditioning with verbal suggestion group* and the *control group*, respectively (effect size of d = 0.78). Based on these means and standard deviations, sample size calculations were done using G\*power 3.1. We simplified the analyses of the main hypotheses, Univariate analyses of variance (ANOVA's) with Dunnett contrasts, into two two-tailed independent samples t-tests (i.e., comparing the positive expectation induction group with the negative expectation induction group and the neutral expectation induction group separately) using a Bonferroni correction. For these t-tests, the means and standard deviations of the most conservative comparison in the present study were used, i.e., of the positive expectation induction with the neutral expectation induction. With an effect size of d = 0.78, an alpha of 0.025 and a desired power of 0.80, this resulted in an estimated total sample size of 33 participants per group.

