### 8.2 Randomisation, blinding and treatment allocation

After part I, in which all participants are exposed to the same procedure, in part II participants will be randomly allocated to one of three experimental groups (see section 3. Study design and Fig 1.). We will use a single blind design: Since the instructions given to the subjects differ in accordance with the group the subjects are allocated to, only subjects will be blinded for the randomization to different groups. No indications for breaking the randomization code are indicated.

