#### 10. STATISTICAL ANALYSIS

### 10.1 Primary study parameter(s)

All variables are continuous. Descriptive statistics (means, standard deviations, etc.) will be calculated of all relevant variables. Variables will be checked for outliers and skewness as these can severely limit the usefulness of the mean as measure for location.

In consultation with the statistician associated with the study ([name]), our main hypothesis, that the induced levels of itch (VAS) will be lower after a positive expectation induction (low-itch expectation induction) (group 1), in comparison to a negative expectation induction (high-itch expectation induction) (group 2), or neutral expectation induction (group 3), will be tested in an ANOVA using Dunnett contrasts for comparing the expectancy effect on itch in group 1 with the effect in group 2 and group 3.

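### The colour arrangement set before the Part II randomisation is absent from the stated primary ANOVA; adding it as a two-level factor is a nearly free gain in precision

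*Protocol*

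**What the plan says.** The Summary defines the main endpoint, taken from the Part II test trials, as "the difference in the levels of itch (VAS scores) evoked by the electrical stimuli associated with the conditioned cues versus the neutral cues". This is a within-person difference score.

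Section 8.3 (Expectation induction) counterbalances colour: "For half of the participants the first colored cue is the conditioned cue and the second colored cue is the neutral cue", with the reverse for the others. It does not say whether the halves are formed over the whole sample or within each group.

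Everyone is conditioned in Part I. Section 3 keeps the same conditioned colour for group 1 in Part II and repeats the Part I procedure for group 2. A participant's arrangement is therefore known before Part II.

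Section 8.2 places allocation after Part I: "in part II participants will be randomly allocated to one of three experimental groups". It names no stratification factor and describes no allocation method.

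Section 10.1 gives the primary analysis as an "ANOVA using Dunnett contrasts for comparing the expectancy effect on itch in group 1 with the effect in group 2 and group 3". Group is the only factor named.

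**The concern.** The endpoint subtracts the rating under one colour from the rating under the other. If one colour draws ratings c points higher than the other whatever its role, each difference score moves by +c or -c according to the arrangement. Swapping the roles stops colour from being confounded with cue role on average. It does not remove this spread from the error term of a model that has group as its only factor.

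The arrangement is assigned by the design and known before randomisation, so it is an obvious candidate for the model. Leaving it out puts precision at stake in both primary contrasts. It does not put their validity at stake.

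**Working it through.** **Inputs from the protocol (Section 4.4).** Planning means (SD) of 0.86 (0.59) and 0.32 (0.79); two-tailed t-tests; "With an effect size of d = 0.78, an alpha of 0.025 and a desired power of 0.80"; 33 per group, so 3 × 33 = 99 in all.

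**Assumption.** A colour effect c of 0.1, 0.2 or 0.3 VAS points, equal in all groups. No section gives a value.

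**1. The plan's own figure.** Pooled SD = √[(0.59² + 0.79²)/2] = √0.4861 = 0.697. Difference = 0.86 − 0.32 = 0.54, so d = 0.54/0.697 = 0.7745. The noncentral t distribution at two-sided 0.025 gives 33 per group for 80% power, with power 0.806 at d = 0.78 and 0.800 at d = 0.7745. The stated 33 is reproduced.

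**2. Chance imbalance, if allocation is not stratified by colour.** With a 50/49 split over 99 participants, the difference between two groups in the share having a given arrangement has SD √(0.25 × 2/33 × 99/98) = 0.124. In 100,000 random permutations the SD was 0.124, and the difference was at least 20 percentage points in 11% of allocations. A difference in share of Δp shifts the contrast by 2cΔp. The SD of that shift is 0.025, 0.050 or 0.074 VAS for c = 0.1, 0.2 or 0.3, against a planned standard error of 0.697 × √(2/33) = 0.172. This shift is not a second loss on top of step 3; it is how the extra variance reaches the contrast.

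**3. Power, for the two readings of the planning SD.**
- Reading A, SD free of colour variance: the unadjusted SD is √(0.697² + c²).
- Reading B, SD already containing it: the unadjusted SD stays at 0.697, and the adjusted SD is √(0.697² − c²).

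| c | A: SD | A: power unadjusted | A: n per group for 80% | B: power unadjusted | B: adjusted SD | B: power adjusted |
|---|---|---|---|---|---|---|
| 0.1 | 0.704 | 0.791 | 34 | 0.800 | 0.690 | 0.809 |
| 0.2 | 0.725 | 0.765 | 36 | 0.800 | 0.668 | 0.836 |
| 0.3 | 0.759 | 0.723 | 39 | 0.800 | 0.629 | 0.880 |

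Under reading A the error variance rises by c²/0.4861, which is 2%, 8% or 19%.

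**4. Simulation of the remedy.** 40,000 trials per cell; three groups of 33; residual SD 0.697 (reading A); one contrast tested at two-sided 0.025. The error is pooled over three groups (96 df), so power at c = 0 is slightly above the 0.800 of step 1.

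| c | Power, no term | Power, term only | Power, term + balance | Type I error, no term | Type I error, balance without term |
|---|---|---|---|---|---|
| 0 | 0.807 | 0.801 | 0.807 | 0.024 | 0.026 |
| 0.1 | 0.794 | 0.803 | 0.806 | 0.023 | 0.024 |
| 0.2 | 0.771 | 0.799 | 0.806 | 0.025 | 0.020 |
| 0.3 | 0.737 | 0.802 | 0.806 | 0.026 | 0.015 |

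The model term does nearly all the work. It costs almost nothing when there is no colour effect. Balance without the term makes the test conservative and recovers little power (0.750 at c = 0.3, against 0.737 with neither).

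**The case against.** The strongest reply is that the protocol contains no error here.

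- **Silence.** A reader might infer that colour is balanced only over the whole sample and that the allocation ignores it. The text does not support that. Section 8.3 does not exclude balance within groups, and Section 8.2 gives no method at all. The imbalance figures hold only if allocation is in fact unstratified. This stands.
- **Power.** A reader might also infer that the trial falls short of its stated 80%. That is not shown. No colour effect is documented. At c = 0.3 the two arrangements differ by 0.6 VAS on the difference score, more than the whole planned effect of 0.54, so the top of the range is generous. The planning SDs come from a previous study of comparable design. If colours were swapped there too, they already contain the colour variance. This stands as well.
- **Validity.** Chance imbalance is not bias. Randomisation keeps the contrasts unbiased, and simulated type I error with colour ignored is 0.023 to 0.026 against 0.025. The counterbalancing still does its main job of separating colour from cue role.
- **Left to the SAP.** A nuisance factor could be added in a statistical analysis plan that is not shown. That is possible, and it is why this is an improvement and not a defect. But the protocol does state its primary model, and group is the only factor in it. Any balancing within groups has to be in the allocation list before the first allocation, which a later analysis plan cannot supply.

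**Conclusion.** This is a minor point about precision. The stated primary ANOVA omits a two-level factor that the design itself assigns before randomisation. Bias and type I error are not at issue.

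The size depends on an undocumented colour effect. Under reading A, the loss is about 1 power point at 0.1 VAS, 3 to 4 at 0.2 and 7 to 8 at 0.3. Under reading B, nothing is lost against the plan, and the gain forgone is about 1, 4 or 8 points. With no colour effect the term makes practically no difference. In either case adding it is worthwhile, because the possible gain far exceeds the cost.

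**What to change.** In Section 10.1, add colour arrangement (which colour is the conditioned cue) as a two-level factor to the primary ANOVA, keeping the Dunnett contrasts for group. This uses 1 of 96 error degrees of freedom.

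In Section 8.2, state whether the arrangement is balanced within groups. Where the allocation list allows, stratify the Part II allocation by the arrangement set in Part I, giving 17/16 in each group of 33. Do this only together with the model term. The cost is a stratified list, with no extra participants or procedures.

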### Low-itch expectation induction

For the low-itch expectation induction, the intensity (mA) of the stimuli will be decreased following the presentation of the conditioned cue (*expectation for low itch*) in comparison to the intensity of stimuli following the neutral cue, which is not adjusted (*neutral expectation*). In line, participants will be told that: "The specific colored cue will signal the activation of the third electrode that induces a decrease in the intensity of the itch stimulus (*expectation for low itch*). The other cue will indicate that the third electrode is turned off and will not change the intensity of the itch stimulus (*neutral expectation*)".

#### Neutral expectation induction

In the neutral group, participants will not receive a conditioning procedure or verbal suggestions; the different colored lights are randomly shown with previously defined random stimuli intensities and participants are merely told that a colored cue will indicate the start of a new stimulus.

Participants are asked to rate their levels of itch on a Visual Analogue Scale (VAS) ranging from 0 (no itch at all) to 10 (worst itch imaginable) after each stimulus. Additionally, participants are videotaped to record scratching behavior of the participants during the experimental sessions.

## Somatosensory stimuli

Itch sensations are induced by two cutaneous electrodes applied on the forearm. A third and inactive electrode is placed between the two active electrodes and represents the sham treatment designed to induce expectations of stimulus alterations. Itch thresholds will be determined according to the protocol of our previous study [25], which was based on the protocol of Colloca [18,19], to apply stimuli with strengths adjusted to participant's individual sensitivity levels. This method showed good validity in our previous study on itch [25]. These threshold measures will be used to adjust the intensity (mA) of the stimuli for conditioning of expectations with regard to itch.

In addition, histamine iontophoresis, previously applied by our research group [1-3,20,21], will be applied to test possible generalization of expectancy effects to other types of itch stimuli. A 0.3% diphosphate histamine solution will be used in the present study. Each participant will undergo one histamine application at the inner side of the forearm, while the conditioned cue (group 1 and 2) or a neutral cue (group 3) will be presented on the computer screen.

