## 8.1.2 Secondary study parameters/endpoints

The secondary study endpoints of the present experiment are: a) the scratching behavior of the participants, b) the levels of itch (VAS ratings) induced by histamine iontophoresis after displaying the conditioned cue, c) the scores on several questionnaires measuring individual characteristics related to expectancy effects, d) the 5-HTTLPR genotype and possibly also other genetic variants.

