### 10.2 Secondary study parameter(s)

Similarly to the primary outcome measure, ANOVAs will be conducted for the secondary outcome measures with regard to expectancy effects on histamine evoked itch, scratching behavior, and genotype. Additionally, Pearson correlation coefficients will be calculated between the individual characteristics and the expectancy effects on itch.

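### Histamine itch is rated once under one cue, so its ANOVA compares raw VAS levels between groups; adjusting for a Part I rating would improve precision at almost no cost

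*Protocol*

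**What the plan says.** The primary endpoint is a contrast within each participant. The Summary puts it this way: "The main study endpoint is the difference in the levels of itch (VAS scores) evoked by the electrical stimuli associated with the conditioned cues", set against the neutral cues, in the testing phase of Part II. Section 10.1 analyses it by ANOVA with Dunnett contrasts of group 1 against groups 2 and 3, and names no covariate.

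The histamine endpoint is built differently. Section 8.3 (Somatosensory stimuli) says "Each participant will undergo one histamine application at the inner side of the forearm". On what the participant sees at that moment, the same sentence adds: "while the conditioned cue (group 1 and 2) or a neutral cue (group 3) will be presented on the computer screen". Section 8.1.2 defines the endpoint as "the levels of itch (VAS ratings) induced by histamine iontophoresis after displaying the conditioned cue", which is a level and not a difference. Section 10.2 then says: "Similarly to the primary outcome measure, ANOVAs will be conducted for the secondary outcome measures with regard to expectancy effects on histamine evoked itch".

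Three other places matter. Section 8.3 has a VAS rating after each stimulus. The Summary describes a Part I testing phase in which both cues are paired with medium-intensity stimuli. Section 8.2 places randomisation after Part I.

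**The concern.** A within-person difference takes out much of what makes one participant's ratings generally higher than another's, such as itch sensitivity and use of the scale. The primary endpoint has that protection. The histamine endpoint does not, because nobody rates histamine under both cues. Carrying the primary model over to histamine therefore means comparing raw VAS levels, with all between-person variation left in the error term.

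Two things are at stake. One is precision on generalisation to another itch stimulus, which is a named secondary objective and the purpose of Part III. The other is labelling: section 10.2 speaks of expectancy effects on histamine itch, and a reader could take that as the conditioned-versus-neutral quantity of the primary analysis, which this design does not yield for histamine.

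**Working it through.** **1. Can a within-person histamine effect be formed?** No. Section 8.3 gives one application under one cue. The only group comparison available is of histamine VAS levels.

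**2. Is there a valid baseline covariate?** Yes. Neutral-cue VAS in the Part I testing phase is rated by all participants under the same procedure and precedes randomisation. Part II ratings would not serve, because they follow allocation and are affected by the induction.

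**3. The plan's own figure.** Section 4.4 gives means 0.86 and 0.32 and SDs 0.59 and 0.79.

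- d = (0.86 − 0.32) / √[(0.59² + 0.79²)/2] = 0.54 / 0.697 = 0.77 (stated: 0.78).
- A two-sided t-test at alpha 0.025 with 80% power, by the noncentral t, gives 33 per group. Power at 33 is 0.806 for d = 0.78 and 0.800 for d = 0.7745.

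The stated 33 reproduces. The means and SDs behind it are placebo-effect scores, not raw VAS levels, and the protocol gives no SD for raw histamine VAS.

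**4. Gain from adjustment.** Let r be the within-group correlation between the Part I neutral-cue mean and histamine VAS. It is not in the protocol, so a range is assumed. The residual variance is (1 − r²) times the raw variance, the standard error is multiplied by √(1 − r²), and the equivalent sample size by 1/(1 − r²). The detectable difference is for one pairwise comparison at 33 per group, two-sided alpha 0.025 and 80% power: 0.774 × √(1 − r²) raw SDs, ignoring the lost degree of freedom.

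| r (assumed) | 1 − r² | SE factor | SE reduction | Equivalent n factor | Equivalent n per group | Detectable difference (raw SD) |
|---|---|---|---|---|---|---|
| 0 | 1.00 | 1.000 | 0% | 1.00 | 33 | 0.77 |
| 0.3 | 0.91 | 0.954 | 5% | 1.10 | 36 | 0.74 |
| 0.4 | 0.84 | 0.917 | 8% | 1.19 | 39 | 0.71 |
| 0.5 | 0.75 | 0.866 | 13% | 1.33 | 44 | 0.67 |
| 0.6 | 0.64 | 0.800 | 20% | 1.56 | 52 | 0.62 |

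At r = 0 the cost is one error degree of freedom: 99 − 3 = 96 becomes 95.

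**5. Why ANCOVA and not a change score.** With equal SDs, subtracting the baseline gives a variance factor of 2(1 − r): 1.4 at r = 0.3 and 1.0 at r = 0.5. It loses precision whenever r is below 0.5. ANCOVA does not, apart from the degree of freedom.

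**6. How far adjustment goes.** As an illustration only, suppose a 0.54-point difference in histamine VAS and raw SDs of 1.0, 1.5 and 2.0, all assumed. Pairwise power at 33 per group is 0.46, 0.21 and 0.12 unadjusted, and 0.60, 0.28 and 0.16 with r = 0.5.

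**7. The cue.** Section 3 and section 8.1.2 describe histamine with the conditioned cue and make no exception for a group. Section 8.3 gives group 3 a neutral cue. If 8.3 holds, group 1 versus group 3 differs in the cue shown as well as in the induction.

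**The case against.** The strongest reply is that nothing stated here is invalid. Allocation is random, so an unadjusted comparison of histamine VAS is unbiased with correct error rates. The objective is exploratory, section 4.4 claims power only for the main hypotheses, and precision covariates are often left to a statistical analysis plan, which is not shown. Section 8.1.2 already defines the endpoint as a level. All of this stands, and it limits the point to precision and labelling. It does not dispose of it, because section 10.2 does fix a model by reference to the primary one, and that model suits a difference score better than a single level.

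The covariate may also be weak. Electrical stimuli are set to each person's own sensitivity, whereas histamine is 0.3% for everyone. Calibration may take out much of the sensitivity that the covariate would need to carry, leaving mainly scale use. That also stands, and it makes the lower rows of r more plausible than the upper ones.

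Stronger readings are tempting and not supported:

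- **That adjustment would remove person-to-person differences.** It removes a fraction r² of the variance, which is 9% at r = 0.3.
- **That raw itch levels vary far more than difference scores.** The protocol gives no SD for raw VAS, so this cannot be shown.
- **That an unadjusted null result would be uninformative.** This needs the missing SD. If it were true, step 6 shows that adjustment would only partly mend it.
- **That the sample size is wrong for histamine.** The protocol never applies it there.

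**Conclusion.** The point holds as an improvement in precision and labelling. It is neither a bias nor an error in a stated figure. As planned, the histamine ANOVA compares raw VAS levels between groups and leaves a suitable pre-randomisation rating out of the model. For an assumed r of 0.3 to 0.6, using that rating would cut the standard error by 5 to 20%, equivalent to 10 to 56% more participants. The gain may well lie at the low end because of the calibration. The result rests on the assumed r, on a linear relation between covariate and outcome, and on Part I ratings being kept per stimulus and cue.

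The disagreement over the cue shown to group 3 is a separate matter within the protocol. The covariate does nothing for it.

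**What to change.** - In section 10.2, specify that histamine VAS is analysed by ANCOVA on group, adjusted for the participant's mean neutral-cue VAS in the Part I testing phase, with the same two Dunnett contrasts (group 1 versus 2, group 1 versus 3). The individual itch threshold, also measured for every participant, may be added as a second covariate for one further degree of freedom. It may carry part of the sensitivity that calibration removes from the electrical ratings.
- Describe the result as a between-group difference in histamine itch level, not as a conditioned-versus-neutral expectancy effect.
- Reconcile sections 3 and 8.1.2 with section 8.3 on the cue shown to group 3, and word the interpretation of group 1 versus group 3 to match.

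The cost is a few sentences, settled before outcome data are examined. No extra histamine application, measurement or participant is needed. If r is zero, one degree of freedom is lost for the main covariate.

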#### 3. STUDY DESIGN

Participants will complete online validated questionnaires at home which will take about 30 minutes, and will visit the department of Health, Medical & Neuropsychology of the Leiden University once, for approximately 5,5 hours. The experiment will take place in a research lab of the department.

The experiment consists of three parts (see Fig. 1 for an overview of the components of the study). In part I and II, expectations with regard to electrically evoked itch will be induced by conditioning with verbal suggestion. Individual itch thresholds are used for determining the intensity of the itch stimuli for the conditioning procedure. In part I of the experiment, all participants will be subjected to a high-itch expectation induction, in order to attain negative expectations with regard to itch as a starting point. In part II of the experiment, participants are assigned to either the experimental group, in which low-itch expectations will be induced (group 1), or one of the control groups in which either once more high-itch expectations will be induced (group 2), or neutral expectations (group 3). Participants will be asked to report their level of itch for every stimulus on a Visual Analogue Scale (VAS), and scratching behavior of the participants will be recorded during the experiment. In part III, histamine iontophoresis will be applied (with the conditioned colored cue displayed on the computer screen) and in addition participants are asked to spit in a special tube to collect saliva for DNA isolation.

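### Section 8.3 shows group 3 a neutral cue during histamine where sections 3 and 8.1.2 specify the conditioned cue, so histamine contrasts with group 3 mix induction and cue type

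*Protocol*

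**What the plan says.** Three places in the Protocol state which cue is on the screen during histamine.

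- Section 3, on Part III: "In part III, histamine iontophoresis will be applied (with the conditioned colored cue displayed on the computer screen". No group is exempted.
- Section 8.1.2, secondary endpoint b: "the levels of itch (VAS ratings) induced by histamine iontophoresis after displaying the conditioned cue". Again no group is exempted.
- Section 8.3, Somatosensory stimuli: histamine is given "while the conditioned cue (group 1 and 2) or a neutral cue (group 3) will be presented on the computer screen".

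The same paragraph of section 8.3 fixes the number of applications: "Each participant will undergo one histamine application at the inner side of the forearm".

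For the analysis, section 10.2 says that "ANOVAs will be conducted for the secondary outcome measures with regard to expectancy effects on histamine evoked itch, scratching behavior, and genotype", on the same lines as the primary outcome. Section 10.1 describes that model as an "ANOVA using Dunnett contrasts for comparing the expectancy effect on itch in group 1 with the effect in group 2 and group 3".

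**The concern.** Staff cannot follow all three statements. Read literally, a group 3 participant handled as section 8.3 directs never yields the endpoint that section 8.1.2 defines.

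The conflict also bears on what the contrast means. The trial asks whether an induced nocebo response can be modified, and secondary objective b carries the expectancy question over to histamine itch. Group 3 is the control that has Part I conditioning and no counter-induction in Part II. If its members see a neutral cue in Part III, whatever is left of their nocebo response is not called up, and group 1 is compared with a control that differs from it in cue as well as in induction. This is settled by the stimulus delivered on the day, so a later analysis plan cannot repair it.

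**Working it through.** There is no stated figure to reproduce for the histamine endpoint, so the check is mainly a comparison of texts.

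**Step 1. Cue shown during histamine, by section.**

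| Protocol section | Groups 1 and 2 | Group 3 |
|---|---|---|
| 3, Part III | conditioned | conditioned (no exception made) |
| 8.1.2, endpoint b | conditioned | conditioned (no exception made) |
| 8.3, Somatosensory stimuli | conditioned | neutral |

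**Step 2. Does group 3 have a conditioned cue?** Yes. Section 3 states: "In part I of the experiment, all participants will be subjected to a high-itch expectation induction". The primary endpoint in section 8.1.1 compares conditioned with neutral cues in Part II, and section 10.1 tests it for group 1 against group 3. The plan itself therefore treats group 3 as having both kinds of cue.

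**Step 3. Can cue and induction be separated?** Each participant has one histamine application, so there is no within-person comparison of cues. Under section 8.3 the cue is fully determined by group: nobody in group 3 sees the conditioned cue, and nobody in groups 1 or 2 sees the neutral one. A cue term cannot be estimated alongside the group terms.

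**Step 4. Direction of the bias.** Write mean histamine itch as follows:

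- m: group 3 under its neutral cue
- m + r3: group 3 under its Part I conditioned cue, where r3 is the nocebo effect remaining after the neutral Part II procedure
- m + r1 and m + r2: groups 1 and 2 under the conditioned cue

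| Contrast | Conditioned cue for all | Section 8.3 as written | Change |
|---|---|---|---|
| Group 3 minus group 1 | (m + r3) − (m + r1) = r3 − r1 | m − (m + r1) = −r1 | smaller by r3 |
| Group 2 minus group 3 | (m + r2) − (m + r3) = r2 − r3 | (m + r2) − m = r2 | larger by r3 |
| Group 2 minus group 1 | r2 − r1 | r2 − r1 | none |

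Suppose r3 is positive and the low-itch induction removes the nocebo response completely without going further, so that r1 = 0. With the conditioned cue for everyone, the contrast is r3. Under section 8.3 it is 0. A null result is therefore compatible with a fully successful modification. In the other direction, if −r1 is above 0 and r3 is not negative, then r3 − r1 is at least as large. Lower itch in group 1 would thus be found in spite of the bias.

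**Step 5. Size.** The bias equals r3. The Protocol gives no value for r3 and no standard deviation for histamine itch. Its only planning figures are in section 4.4 and concern the primary endpoint: 0.86 (SD 0.59) against 0.32 (SD 0.79).

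- Pooled SD = √((0.59² + 0.79²)/2) = 0.697.
- d = 0.54/0.697 = 0.775, against the stated 0.78.
- Two-sided alpha 0.025 and power 0.80 by the noncentral t give 32.5 per group for d = 0.78 and 32.98 for the unrounded d. Both round up to the stated 33.

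The planned sample size reproduces, and nothing in it depends on the cue shown in Part III.

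**The case against.** The best defence is that the neutral cue is intended. Section 8.3 is the detailed procedure and the other two sections are brief summaries. A group with a neutral expectation, shown a neutral cue, is a recognisable comparator for a positive expectation. Objective b speaks only of expectancy effects on histamine itch and does not name the cue that once signalled high itch. This stands as a possible intention. However, the Protocol gives no such rationale, and sections 3 and 8.1.2 would then be wrong instead.

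A second defence is that after Part II either colour counts as neutral for group 3, whose members are told only that a cue marks the start of a stimulus. That would leave the colour shown to group 3 undefined, and it still conflicts with the two sections that name the conditioned cue.

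Two stronger readings are tempting, and the documents do not support either.

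- A reader might infer that the histamine comparison is uninterpretable whatever it shows. Group 1 versus group 2 uses the same cue and is untouched. By Step 4, a finding of lower itch in group 1 than in group 3 would be conservative if a nocebo effect remains.
- A reader might put the section 4.4 figures to work and state a loss of power. Those figures are placebo effects from an earlier study, used to plan the electrical-itch endpoint, which is a difference between cues. Histamine itch comes from one application under one cue, and its spread is not given. Section 4.4 also describes no nocebo induction before that earlier comparison. The 0.54 difference may therefore correspond to −r1 rather than to r3 − r1, in which case the neutral cue would forgo a gain rather than cause a loss. Any power figure would rest on assumptions that the Protocol does not supply.

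**Conclusion.** The text is wrong as written: section 8.3 contradicts sections 3 and 8.1.2 on the cue shown to group 3. If section 8.3 is followed, the group 1 versus group 3 histamine contrast, and group 2 versus group 3 if it is made, mixes the Part II induction with the type of cue. That much needs no numerical assumption.

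The direction of the bias rests on one assumption, that some Part I nocebo effect persists in group 3 after the neutral Part II procedure. In that case the 1-versus-3 difference shrinks by the size of the remnant, and a null result cannot be read as absence of an effect. If nothing persists, the bias is zero, but the design offers no way to find that out for histamine. The amount cannot be computed from the Protocol.

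Severity is moderate. The matter touches contrasts with group 3 on one secondary, exploratory endpoint. The primary endpoint is measured in Part II, before histamine is given, and neither it nor the sample size is affected.

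**What to change.** Reconcile sections 3, 8.1.2 and 8.3 before enrolment, so that the cue shown to group 3 is stated in the same way throughout.

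- **Preferred:** show each participant's own Part I conditioned cue during histamine in all three groups. This means deleting the clause in section 8.3 that gives group 3 a neutral cue. The word *own* matters because the colours are counterbalanced across participants. This agrees with the two other sections and removes the confounding.
- **If the neutral cue is deliberate:** amend sections 3 and 8.1.2 to say so, identify which colour group 3 sees, and state that any histamine contrast with group 3 estimates the combined effect of induction and cue.

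The preferred change costs one clause of text and, presumably, a change to what the screen displays for group 3. It adds no participants and no procedures. If the ethics committee has already given a favourable opinion, the change is an amendment to be handled under section 12.3.
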